## **5. PLANNED ANALYSES**

### **5.1. Interim Analyses**

DMC meetings will occur after the first 10 subjects have completed 12 weeks of treatment and every 12 weeks thereafter until the last enrolled subject completes 48 weeks, or as DMC meetings are conducted in concert for related BCX7353 studies.

Before each scheduled DMC meeting, a packet of summary materials will be prepared and distributed for the Committee's review. The packet will include study disposition, demographic, and safety information by treatment group. Study disposition will consist of the number of subjects screened, the number of subjects allocated to treatment, the number of subjects who received treatment, the number of subjects who completed the study, the number of subjects who were withdrawn from the study and the primary reasons for withdrawal, the number of subjects ongoing in the study, the number of subjects who completed dosing in the entire study, the number of subjects withdrawn from the study medication, and the primary reasons for withdrawal, and the number of subjects ongoing on study medication. Demographic information will consist of age, gender, race, ethnicity, weight, height, and body mass index (BMI).

Safety summaries will include an overall summary of TEAEs (overall numbers of subjects with TESAEs, TEAEs, drug-related TEAEs, TEAEs leading to discontinuation of study drug, Grade 3 or 4 TEAEs, and drug-related TEAEs of Grade 3 or 4), summaries of TEAEs by system organ class (SOC) and preferred term (PT), which include TESAEs, TEAEs, Grade 3 or 4 TEAEs, TEAEs leading to discontinuation of study drug, and summaries of subjects with treatment-emergent laboratory abnormalities overall and for each laboratory panel by parameter and grade. Relevant review materials will normally be sent to DMC members and open session participants 5 business days before each scheduled meeting.

All summary materials will be distributed via email.

An internal analysis will be conducted at the time of the BCX7353-302, Part 1 analysis. This analysis will be used to write the draft report for the BCX7353-204 study.

An interim analysis will be performed when approximately 100 subjects at either the 110 or 150 mg dose from a combination of studies BCX7353-204 and BCX7353-302 complete 48 weeks. Additionally, an integrated analysis of safety and effectiveness involving data from both studies will be performed. This analysis will be used for regulatory submissions.

Other interim analyses may be performed as needed during the course of the study to support regulatory filings and safety updates at the request of the Sponsor.

### **5.2. Final Analyses**

The final analysis will be completed after the last subject completes the final study visit or discontinues the study and the resulting clinical database has been cleaned, quality checked, locked, and authorized for analysis.

## 6. GENERAL CONSIDERATIONS FOR DATA ANALYSES AND HANDLING

### 6.1. General Summary Table and Individual Subject Data Listing Considerations

Tables and listings will be prepared in accordance with the current ICH Guidelines (ICH E3 Structure and Content of Clinical Study Reports 1996). The information and explanatory notes in the “footer” or bottom of each table and listing will include the following information:

- Date of data extraction
- Date of output generation
- Statistical Analysis Software (SAS®) program name, including the path where the program is stored
- Any other output specific details that require further elaboration

In general, tables will be formatted with columns displaying findings for all subjects by treatment group and all subjects across treatment groups.

Version 9.4 or higher of the SAS system will be used to analyze the data and to generate tables, figures, and listings. All SAS programs prepared to analyze the data will be properly annotated so as to permit uninvolved outside statistical experts to replicate all the analyses specified in this SAP.

These listings will generally be sorted by treatment group, subject identifier, and visit, if applicable.

Summary displays will be presented by treatment. A column that combines both active treatments will also be included. [Table 4](#) shows treatment descriptors for displays.

**Table 4: Treatment Descriptors for Displays**

Sort Order	Treatment	Notes
1	BCX7353 110 mg	110 mg
2	BCX7353 150 mg	150 mg
3	Total	Combined 110 mg and 150 mg groups

Summary tables for medications and free-text fields for HAE medication history are coded according to the World Health Organization Drug Dictionary (WHODD) from March 2017. AE PTs and body/organ systems are coded using the Medical Dictionary for Regulatory Activities (MedDRA) version 19.1.

## **6.2. General Post Text Summary Table and Individual Subject Data Listing Format Considerations**

Tables, listings, and figures will be numbered using a decimal system to indicate the main levels of unique displays and sub-levels of replicate displays. The first level represents the appendix within which the tables, figures, and listings will appear. This will be 14 for tables and figures and 16 for listings. For tables, the second level of the numbering represents the type of data; 1 for Study Population, 2 for Effectiveness, 3 for Safety, 4 for Health Outcomes, and 5 for pharmacokinetics (PK). The third level of numbering represents the type of endpoint within the data type, the fourth represents a count of displays for the endpoint, and the fifth level is used for repeated tables. For example, tables may be repeated using a different population or for a subset of subjects.

Secondary titles will be used to identify the analysis population used for the displays.

Listings will be numbered starting with 16.2.1 and with sequential numbering in the third level in accordance with ICH guidelines. Listings will be sorted and presented by dose, subject number, and visit, if applicable.

## **6.3. Data Management**

A data management plan will be developed and approved prior to data entry. Data will be captured using the Medidata electronic data capture system. Electronic validation steps (edit checks) will be utilized, and data cleaning will occur in conjunction with each site. Prior to transfer of data provided by vendors (eg, laboratory data), a data transfer agreement including specifications for the type of file, definitions of variables, and contact information for the sending and receiving parties will be developed and finalized. PharPoint standard operating procedures (SOPs) will be used.

Data will be mapped to Study Data Tabulation Model (SDTM)-compliant datasets prior to creation of Analysis Data Model (ADaM)-compliant derived datasets for use in the creation of summary tables. All analyses will be generated using SAS version 9.4 or above and in accordance with PharPoint SOPs.

## **6.4. Data Presentation Conventions**

Continuous variables (eg, age) are summarized using descriptive statistics (the number of subjects with available data, the mean, standard deviation (SD), median and minimum and maximum). Categorical variables (eg, race) are summarized using counts and percentages. Percentages are calculated using the total subjects per treatment group.

The following conventions are applied to all data presentations and summaries.

- For continuous variables, all mean and median values are formatted to 1 more decimal place than the measured value. SD values are formatted to 2 more decimal places than the measured value. Minimum and maximum values are presented with the same number of decimal places as the measured value.
- For categorical variables, the number and percentage of responses are presented in the form XX (XX.X%) where the percentage is in the parentheses.

- Date variables are formatted as DDMMYYYY for presentation. Time is formatted in military time as HH:MM for presentation.
- Wherever possible, data will be decimal aligned.

The table of contents as part of this SAP along with the table and listing shells provided in separate documents provide the expected layout and titles of the tables, listings and figures. Any changes to format, layout, titles, numbering, or any other minor deviation will not necessitate a revision to the SAP, nor will they be considered as deviations from planned analyses. Only true differences in the analysis methods or data handling will necessitate such documentation. The appropriate listings supporting the tables will be included and are not necessarily specified in the individual sections throughout the document.

## **6.5. Analysis Populations**

### **6.5.1. Screen Failures**

Subjects who give informed written consent, but are not allocated to study treatment, and are noted as screen failures in eCRF are considered screen failures. These subjects will not be treated with study drug and will not be summarized other than on the disposition table. Data collected from screen failures may be presented on corresponding data listings.

### **6.5.2. Safety Population**

The safety population will include all subjects who receive at least 1 dose of study drug. This population will be used in the assessment and reporting of demographic information, baseline disease characteristics, safety data, and PK concentrations. Data will be analyzed according to the actual treatment received on Day 1 of the study.

## **6.6. Baseline Definition**

Baseline is the last available assessment prior to the time of first dose unless otherwise specified.

### **6.6.1. Baseline Attack Rate**

No baseline attack rate is calculated for the following reasons:

- Not all subjects entering the study have baseline measures collected as some subjects are rolling over from previous studies.
- Some subjects are on other prophylactic HAE medications
- Some subjects are discontinuing androgens that were used as HAE prophylaxis

## **6.7. Derived and Transformed Data**

### **6.7.1. Baseline Age**

Age in years will be reported as recorded on the demographics form.

### **6.7.2. Study Day**

Study Day 1 is defined as the date of first dose.

If the date of interest occurs on or after the first dose date, study day will be calculated as (date of interest – date of first dose + 1). If the date of interest occurs prior to the first dose date, study day will be calculated as (date of interest – date of first dose). There is no study day 0.

### **6.7.3. Change from Baseline**

Change from baseline is calculated as (post-baseline result – baseline result).

Percent change from baseline is calculated as ((change from baseline/baseline result) × 100).

If either the baseline or the post-baseline result is missing, the change from baseline and/or percent change from baseline will be set to missing as well.

### **6.7.4. Prior Androgen Use**

Subgroup analyses for prior androgen use (latency and duration) are described in Section 9.2. Details of calculations for latency and duration are described in this section.

Any medications classified as androgens or androgen derivatives (based on WHODD, March 2017) used prior to the study treatment start date will be considered “prior androgens”. These medications will include androgens (unspecified), oxandrolone, danazol (brand name = Danocrine), and stanozolol.

Total duration of prior androgen use includes days from beginning of first date of each androgen used to last dosing date of each androgen. Any days of overlapping multiple androgen use will be counted once for total duration.

Total duration of prior androgen use within the 12 months prior to treatment start date will be calculated similarly to total duration of prior androgen use. The prior 12-month window will include days from treatment start date minus 365 up to treatment start date. For androgens started prior to treatment start date minus 365, start date of androgen will be considered treatment start date minus 365 for this analysis. Duration will be calculated as stop date – start date + 1. If androgen was started and stopped on the same day, duration will be 1 day.

Days since stopping last androgen use (latency) are calculated as date of last androgen use - treatment start date.

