The most common clinically significant chemistry abnormalities were liver-related abnormalities, and the most common abnormality was ALT increased. The majority of treatment-emergent liver abnormalities were Grade 1 or 2; however, 13 subjects (5.7%) experienced a treatment-emergent Grade 3 or 4 ALT laboratory abnormality, and all of these subjects had previously used androgens. All but 1 subject with a Grade 3 or 4 ALT stopped androgens 7 to 9 days from first dose of BCX7353; 1 subject stopped androgens < 2 months from the first dose of BCX7353. No subject had synthetic dysfunction or evidence of hepatitis. Subjects were mostly asymptomatic, although a few subjects had abdominal symptoms that overlapped with the GI symptoms reported with BCX7353 treatment; no subject had signs or symptoms of acute hepatitis. The Grade 3 or 4 ALT elevations in the 13 subjects were primarily laboratory abnormalities without clinical symptoms. All 13 subjects improved or recovered, 5 subjects while continuing on BCX7353; 2 subjects subsequently discontinued study drug for unrelated reasons (perceived lack of efficacy in both subjects). A total of 15 subjects had postbaseline ALT > 3 × upper limit of normal (ULN; 2 subjects with nontreatment emergent ALT values). Of the subjects who had stopped androgens within the previous 2 weeks before initiating BCX7353, the incidence of subjects with ALT > 3 × ULN was 32.5%. Of the subjects with ≥ 5 years of androgen use, the incidence of subjects with ALT > 3 × ULN was 13.0%. One subject had a bilirubin > 1.5 × ULN although no subject had a Grade 3 or Grade 4 bilirubin, and no subject had a concurrent elevation in bilirubin > 1.5 × ULN and ALT or AST > 3 × ULN. No subject met the criteria for Hy's law during the study.

In summary, BCX7353 was safe and generally well tolerated with no new safety signals observed.

Subjects treated with BCX7353 110 or 150 mg QD had durably low attack rates, with no evidence for the development of tolerance to BCX7353. After 1 month of treatment, the 73 subjects in the BCX7353 150 mg dose group who received BCX7353 through Week 48 had a mean (SD) attack rate of 1.18 (1.40) attacks per month. The mean rate of attacks held relatively steady during Months 2 to 12: 1.01 (1.26) attacks per month in Month 6 and 0.81 (1.03) attack per month in Month 12.

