## **7. STUDY POPULATION**

### **7.1. Subjects Disposition**

Subject disposition will be presented for all subjects. The number of subjects who completed through each study visit and those that discontinued from the study will be provided. The primary reasons for early discontinuation will also be presented by dose. Reasons for exclusion from the safety population will be tabulated. Days on study will be summarized by treatment group.

Subject status at the end of the study will be listed and summarized based on the safety population, showing the number and percentage of subjects with early discontinuation of study treatment and early withdrawal from the study along with reasons for each item. The listings will include whether subjects discontinued from the study drug, whether they withdrew from the study and the reasons for the discontinuation of study drug, along with the date of first and last dose and the date of completion or discontinuation from the study drug and date of study withdrawal. Duration on study treatment and on the study will also be provided.

A consolidated standards of reporting trials (CONSORT) diagram will be created based on the summary tables for the study report. This will include summary tables assessed for eligibility, subjects excluded (not meeting entrance criteria, declining to participate, and other reasons for exclusion), subjects enrolled, subjects allocated to either treatment group, including subjects who did and did not receive intended treatment (with reasons given for not receiving intended treatment), subjects lost to follow-up or discontinuing treatment (with reasons given), and subjects analyzed vs. not analyzed (with reasons given for subjects who are not included in an analysis).

A summary of enrollment by country and investigator site will be provided. Early discontinuation will be summarized by country and investigator site.

Summaries of prior androgen use will be provided by overall duration of prior use, duration of use within 12 months prior to treatment start date, and time since stopping androgen use to treatment start date (latency).

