### **9.2. Subgroup Analyses**

The following subgroup analyses for selected safety endpoints will be performed:

- Prior androgen use (latency: time between stopping androgen and starting BCX7353: < 2 weeks, 2 weeks to < 1 month, 1 month to < 2 months, and  $\geq$  2 months)
- Duration of prior androgen use (never used, < 6 month, 6 months to < 1 year, 1 year to < 5 years, 5 years to < 10 years,  $\geq$  10 years).

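### SAP 6.7.4 can count drug-free gaps between repeat courses of the same androgen as use, and separately gives negative 12-month durations for androgens stopped before the window

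*SAP*

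**What the plan says.** SAP 6.7.4 gives two duration rules for prior androgens.

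- **Total duration.** "Total duration of prior androgen use includes days from beginning of first date of each androgen used to last dosing date of each androgen". One adjustment follows: "Any days of overlapping multiple androgen use will be counted once for total duration". Nothing is said about stopping and restarting the same drug.
- **Duration in the prior 12 months.** "The prior 12-month window will include days from treatment start date minus 365 up to treatment start date". Then: "For androgens started prior to treatment start date minus 365, start date of androgen will be considered treatment start date minus 365". Duration is the stop date minus the start date plus one. No condition is placed on the stop date and no minimum of zero is stated.

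The two results are used in different places. SAP 9.2 names two safety subgroup variables. One is latency and the other is "Duration of prior androgen use (never used, < 6 month, 6 months to < 1 year", with further classes at 1, 5 and 10 years. SAP 9.3.1 repeats all TEAE analyses by subgroup, SAP 9.6 repeats the hepatic laboratory summary by the same subgroups, and SAP 13.1 lists Kaplan-Meier outputs for Grade 3 or 4 ALT, AST and bilirubin by duration. The 12-month measure appears in SAP 7.1, as "duration of use within 12 months prior to treatment start date", in a descriptive summary of prior use.

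**The concern.** A first-to-last span equals exposure only if use was continuous. The protocol's exclusion criterion on oral androgens (8.2.2) covers prophylactic and acute use, and acute use may well be episodic. The SAP's androgen list also has an unspecified category, so separate unspecified courses could be joined into one span.

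Duration of androgen use already carries weight in the safety account. Protocol 5.2.2 links use of at least 5 years to liver-related TEAEs and to Grade 3 or 4 liver-related TEAEs, and reports: "Of the subjects with ≥ 5 years of androgen use, the incidence of subjects with ALT > 3 × ULN was 13.0" per cent. The top class is not small. Protocol 5.2.2 gives 12 lack-of-efficacy discontinuations as 18.2% of users of 10 years or more, which implies about 66 subjects (12 / 0.182 = 65.9). Prior users number 40 + 113 = 153, so this is about 43% of them. If intermittent users are placed in the long-duration classes, the relation between true exposure and liver findings is blurred.

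The 12-month rule raises a lesser issue. Negative day counts would distort the mean, median and minimum of a descriptive summary.

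**Working it through.** The documents give no subject-level androgen dates, so the dates below are illustrative. T is the treatment start date.

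**1. Total duration (rule from SAP 6.7.4, classes from SAP 9.2).** Take two courses, 1 January to 31 December 2005 and 1 January to 30 November 2018.

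- Days covered: 365 + 334 = 699; 699 / 365.25 = 1.91 years.
- First-to-last span: 2005 to 2017 is 13 × 365 + 3 leap days = 4,748; adding 334 gives 5,082; 5,082 / 365.25 = 13.91 years.

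| Situation | Days | Class |
|---|---|---|
| Same drug, rule read per drug | 5,082 | 10 years or more |
| Same drug, rule read per recorded course | 699 | 1 to under 5 years |
| Two different drugs, either reading | 699 | 1 to under 5 years |

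A second pair of courses (1 January 2005 to 30 June 2006, and 1 January 2016 to 30 June 2017) gives 546 + 547 = 1,093 days covered, against a span of 12 × 365 + 3 + 181 = 4,564 days. The class shift is the same. A span is never shorter than the days it contains, so the error runs in one direction only.

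**2. Duration in the prior 12 months (SAP 6.7.4).** Consider an androgen started before T−365 and stopped at T−k. The start is reset to T−365, so the formula gives (T−k) − (T−365) + 1 = 366 − k.

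| Stop date | Formula | Days of use inside the window |
|---|---|---|
| T−7 | 359 | 359 |
| T−365 | 1 | 1 |
| T−366 | 0 | 0 |
| T−367 | −1 | 0 |
| T−400 | −34 | 0 |
| T−730 | −364 | 0 |

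With T = 1 January 2019, a stop on 2 January 2016 (k = 1,095) gives −729, and a stop on 31 December 2010 (k = 2,923) gives −2,557.

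**3. Does the second fault reach the liver subgroups?** The 12-month measure cannot exceed 366 days (about 1.00 year), so it cannot define classes that run to 10 years or more. Those classes must use total duration. A negative 12-month value moves no subject between SAP 9.2 subgroups.

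**4. Illustration of dilution from the first fault.** Suppose a fraction f of the class with at least 5 years of use are really shorter-term users with 2% incidence of ALT > 3 × ULN. Both inputs are assumptions. Incidence in the true long-term users is then (13.0 − 2f) / (1 − f):

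- f = 0.1: 12.8 / 0.9 = 14.2%
- f = 0.2: 12.6 / 0.8 = 15.75%, about 15.8%
- f = 0.3: 12.4 / 0.7 = 17.7%

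These figures show what such a mix would do. They are not estimates for this trial.

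**The case against.** The strongest reply is that the SAP never says gaps count. If each androgen means each recorded entry with its own dates, gaps drop out even for the same drug. The same section's rule that an androgen started and stopped on one day counts as 1 day fits that reading. On the 12-month rule, the window sentence limits the measure to days inside the window, so 0 is plainly intended, and a value such as −2,557 would be noticed on review. The subgroups are descriptive with no formal tests. Detailed androgen listings are planned for subjects with hepatic elevations (SAP 9.6, and listings 16.2.4.3.4 and 16.2.8.12).

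Much of this stands. The per-entry reading is possible, but the text points more naturally to one span per drug, and for the subject above the two readings differ by 12 years. The intended 0 is clear, but the stated formula does not produce it. The listings allow individual histories to be checked but do not correct the tabulated classes.

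A reader might infer that both faults misclassify the liver subgroups. They do not: the 12-month value feeds only SAP 7.1. Nor is every gap between courses counted, because gaps between different androgens are excluded on either reading.

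**Conclusion.** SAP 6.7.4 has two separate derivation faults.

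- **Total duration.** On the per-drug reading, drug-free time between repeat courses of the same androgen counts as use. This can move an intermittent user up across the 5-year and 10-year cut-points of the safety and liver subgroups.
- **12-month duration.** Followed literally, stops at T−367 or earlier give negative days. The effect is confined to the descriptive summary in SAP 7.1.

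It would go too far to say that the subgroups, or the interim figures in Protocol 5.2.2, are in fact misclassified. The documents do not show how many subjects had interrupted courses of one drug, or how the interim classes were programmed. The 14.2% to 17.7% range rests wholly on assumed inputs. The lack-of-efficacy comparison by androgen duration is also not a planned SAP analysis, since SAP 8.2 rules out effectiveness subgroups.

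The wording should still be corrected before database lock, because total duration is one of only two safety subgroup variables and is already used in statements about liver risk.

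**What to change.** Amend SAP 6.7.4 in two places.

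1. *Total duration is the number of distinct calendar days before Day 1 covered by any recorded androgen course, from that course's start date to its stop date. Days between courses are not counted, and overlapping days are counted once.* Add a footnote to the outputs identifying subjects for whom only first and last dates were recorded, since their value remains a span.
2. *For the 12-month duration, each course is restricted to the window. A course that stopped before treatment start minus 365 contributes 0 days.*

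The cost is two sentences and minor reprogramming. The first change depends on course-level dates. The documents do not show that these were collected: Protocol 11.1.1 describes an HAE history questionnaire completed from source records where available, with subject input for the rest. Where the dates are missing the span stays, and the footnote makes that visible. The second change needs no new data.

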Fifty-nine subjects (26.0%) prematurely discontinued study drug; 57 subjects (25.1%) discontinued study drug before 48 weeks of dosing. The most common reasons for discontinuation of study drug were perceived lack of efficacy (12.3%) and laboratory abnormalities or TEAEs (8.4%). Overall, more subjects treated with BCX7353 110 mg compared to BCX7353 150 mg discontinued study drug due to perceived lack of efficacy; 17 of 100 subjects (17.0%) vs. 11 of 127 subjects (8.7%). Overall, 19 subjects (8.4%) discontinued study drug due to TEAEs; 6 (6.0%) and 13 subjects (10.2%) in the BCX7353 110 and 150 mg

dose groups, respectively. TEAEs leading to discontinuation in > 1 subject were ALT increased (4 subjects [1.8%]), upper abdominal pain (3 subjects [1.3%]), vomiting (2 subjects [0.9%]), AST increased (2 subjects [0.9%]), hepatic enzyme increased (2 subjects [0.9%]), and liver function test (LFT) abnormal (2 subjects [0.9%]).

The majority of subjects (91.0% and 90.6% of subjects in the BCX7353 110 and 150 mg dose groups, respectively) had at least 1 TEAE during the study. There was no effect of dose on the incidence of AEs. Overall, the most frequently reported TEAEs were nasopharyngitis (30.8%), headache (17.6%), abdominal pain (13.2%), and diarrhea (13.2%).

Long term prior androgen use of ≥ 5 years and discontinuation of androgens within 2 weeks of BCX7353 initiation were correlated with a higher subject incidence of liver-related TEAEs, but not other types of TEAEs. Subjects who discontinued androgens in the 2 weeks prior to initiating BCX7353 (n = 40) experienced liver-related TEAEs in the investigations SOC more frequently than subjects who discontinued androgens ≥ 2 weeks before initiating BCX7353 (n = 113) or those subjects who had never used androgens (n = 74). In these groups, ALT increased, 25.0% vs. 2.7% and 1.4%, respectively; AST increased 17.5% vs. 2.7% and 1.4%, respectively; hepatic enzyme increased, 2.5% vs. 0.9% and 0, respectively; LFT abnormal, 5.0% vs. 0 and 0; and transaminase increased, 2.5% vs. 0 and 0.

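### SAP 6.7.4 writes androgen latency with the subtraction reversed, and does not say whether the partial-date rules in SAP 6.8.2 apply to it

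*SAP*

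**What the plan says.** SAP 6.7.4 is where the SAP puts the calculations for latency and duration of prior androgen use. For latency it states: "Days since stopping last androgen use (latency) are calculated as date of last androgen use - treatment start date".

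Two other sections describe the same quantity in the opposite direction. SAP 7.1 summarises androgen use by "time since stopping androgen use to treatment start date (latency"). SAP 9.2 forms the latency subgroups from the "time between stopping androgen and starting BCX7353: < 2 weeks, 2 weeks to < 1 month", followed by two longer classes, the last open-ended from 2 months.

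On incomplete dates, 6.7.4 is silent and does not refer to any other section. SAP 6.8.2 does give rules for partial dates of prior and concomitant medication, with no exception for androgens. Its stated purpose is to settle whether a medication was taken during treatment. A stop date without a day goes to the end of the month. A stop date with only a year goes to 31 December, or to trial termination if that falls in the same year. There is no rule for a stop date that is missing altogether.

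**The concern.** Latency and duration of androgen use are the only safety subgroups in SAP 9.2. SAP 9.3.1 repeats the TEAE analyses by subgroup, and SAP 9.6 repeats the hepatic elevation table by prior androgen use. The interim liver findings in Protocol 5.2.2 are described through the same grouping. The line that derives the grouping variable should therefore give the classes it is meant to feed, and as written it does not.

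The partial-date matter is smaller. A rule that takes the latest possible stop date is a reasonable, cautious choice when the question is whether a drug overlapped treatment. When the question is how long before treatment the drug was stopped, the same choice pushes every partial date in one direction, towards a shorter gap.

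**Working it through.** **1. The sign.** Inputs: the formula in SAP 6.7.4, the classes in SAP 9.2, and test gaps between androgen stop and first dose. One month is taken as 30 days and two months as 60 (an assumption; the SAP does not define them for this purpose).

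| Gap before first dose (days) | As written: last use − start | Reversed: start − last use | Class under the reversed form |
|---|---|---|---|
| 7 | -7 | 7 | under 2 weeks |
| 14 | -14 | 14 | 2 weeks to under 1 month |
| 28 | -28 | 28 | 2 weeks to under 1 month |
| 45 | -45 | 45 | 1 to under 2 months |
| 60 | -60 | 60 | 2 months or more |
| 400 | -400 | 400 | 2 months or more |

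The reversed form gives the classes that SAP 9.2 intends. Under the written form every value is negative. A program that tests only for less than 14 days puts all of them in the shortest class; one that also requires a non-negative value puts them in none. Either way, only a stop after first dose could reach a class of 2 weeks or more.

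**2. What the interim report shows.** Protocol 5.2.2 reports two groups of prior users: "Subjects who discontinued androgens in the 2 weeks prior to initiating BCX7353 (n = 40") and "subjects who discontinued androgens ≥ 2 weeks before initiating BCX7353 (n = 113"), plus 74 who never used androgens.

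- 40 + 113 + 74 = 227, the number treated.
- Prior users: 40 + 113 = 153.
- At 2 weeks or more: 113 / 153 = 73.9%.

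The written formula cannot produce a group of 113 at 2 weeks or more before first dose. The interim split therefore rests on the positive interval.

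**3. What a literal run would do (illustration only).** ALT increased is reported in 25.0% of the 40 (10 subjects) and 2.7% of the 113 (about 3 subjects). If all negative values fell in the shortest class, the two groups would merge: (10 + 3) / 153 = 8.5%, in place of 25.0% against 2.7%.

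**4. Partial stop dates, if SAP 6.8.2 were applied.** Example treatment start: 15 June 2018 (assumed), with trial termination in a later year. Latency is start minus imputed stop.

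| Stop as recorded | Imputed stop | Latency (days) |
|---|---|---|
| June 2018 | 30 June 2018 | -15 |
| May 2018 | 31 May 2018 | 15 |
| April 2018 | 30 April 2018 | 46 |
| 2018 | 31 December 2018 | -199 |
| 2017 | 31 December 2017 | 166 |

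Each imputed value is the shortest gap that the recorded part of the date allows, ignoring any knowledge that the stop came before dosing. A stop in April 2018 could truly lie 46 to 75 days before this start; the rule always returns 46. Two of the five rows place the stop after first dose.

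**The case against.** The strongest reply is that this is an editorial slip. The sentence in 6.7.4 is labelled as days since stopping, which fixes its meaning. It points to SAP 9.2, where the direction is clear. The written order also matches the convention in SAP 6.7.2 for dates before first dose: "study day will be calculated as (date of interest – date of first dose). There is no study day 0". A programmer would probably notice, and the interim split shows the intended direction was used. All of this stands, and it is why the point is minor. It does not make the formula right: 6.7.4 is the section that defines the calculation, and the change is one line.

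A reader might go further in four ways that the documents do not support.

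- **That interim or later tables are misclassified.** The 40 / 113 / 74 split speaks against this, and no affected output is shown.
- **That the SAP has no rule for partial androgen dates.** SAP 6.8.2 covers prior medication and does not exclude androgens. What is missing is a statement in 6.7.4 on whether it applies, and a rule for a completely missing stop date.
- **That the reversed formula breaks the aim in SAP 6.1 to "permit uninvolved outside statistical experts to replicate all the analyses specified in this SAP".** That sentence concerns the annotation of SAS programs, not the wording of this derivation, and an outside analyst would also have 7.1 and 9.2.
- **That late imputation has distorted the liver signal.** The number of partial androgen dates is not given. On the 13 subjects with Grade 3 or 4 ALT, Protocol 5.2.2 says: "All but 1 subject with a Grade 3 or 4 ALT stopped androgens 7 to 9 days from first dose of BCX7353". Those dates appear to be known to the day. Imputation also need not change the class: the 2017 row above still gives 166 days, in the longest class.

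**Conclusion.** The point holds and is minor. The subtraction in SAP 6.7.4 is the reverse of 7.1 and 9.2, and read literally it leaves no stop before Day 1 able to reach a class of 2 weeks or more. This follows from the text and needs no assumption. On the interim figures the literal rule would have affected 113 of 153 prior users, but those same figures show it was not followed.

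The partial-date matter is secondary and conditional. It rests on two things the documents do not settle: whether 6.8.2 is meant to apply to androgen latency and duration, and how many androgen dates are incomplete. If it applies, the direction is certain (latency can only shorten, and a stop may land after first dose), but the size is unknown and may be nil.

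**What to change.** In SAP 6.7.4, write: latency = treatment start date minus date of last androgen use.

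In the same section, state whether SAP 6.8.2 applies to androgen latency and duration, and say how a completely missing stop date is handled. Whatever is chosen, an imputed date should not place a stop known to be before dosing on or after first dose. One way is to show subjects whose class cannot be determined as *unknown* and report their number; capping the imputed stop before first dose is another.

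The cost is two lines of SAP text and possibly one extra row in the androgen subgroup tables. No data collection changes. Since the interim split already follows the intended direction, the sign correction should leave those reported groups unchanged.
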